8.1.5 Monitoring Participant Adherence

Adherence at 8 weeks and 6 months will be determined using a 4-point- Likert scale [33] (scored 1 – continued a strict low FODMAP diet; 2 – reintroduced high FODMAP foods to tolerance; 3 – continued a low FODMAP diet 50% of the time; 4 – returned to habitual diet). Analysis of FODMAP content will be via the Comprehensive Nutrition Assessment Questionnaire (CNAQ) [34] in all participants, in order to verify that the FODMAP content is less in the low FODMAP diet arm at 8 weeks, compared with the other four trial arms. The CNAQ is a semi-quantitative food frequency questionnaire validated to assess FODMAP and nutrient intake, and is determined using an online automated entry system (http://www.cnaq.com.au)

Participants who are classed as non-adherent after the 8-week restriction phase will be classed as non-responders and will be instructed to return to their usual diet. This will include any participants who do not respond with an answer of 1, 2, or 3 to the adherence question.

8.1.6 Monitoring Intervention Fidelity

In order to ensure that the low FODMAP dietary intervention is delivered as intended consistently across sites, fidelity will be monitored using a bespoke fidelity check list. This check list covers three domains of setting, knowledge of content, and competency of delivery. This check list will be self-completed by dietitians at all visits, with a random sample of ~10% being assessed to ensure consistency and competency across sites.

8.2 Amitriptyline

8.2.1 Dosage and Duration

Participants randomised to receive amitriptyline will begin treatment at a low dose of 10mg (one tablet) to be taken once daily (OD) at night. Self-led dose titration may occur during the first three weeks of treatment depending on side effects and response to treatment, using the dose guidance document provided. The dose can be increased by 10mg OD per week, to a maximum of 30mg OD at night (three tablets), if there is inadequate improvement in symptoms and no intolerable side effects. Therefore, participants will take 10mg OD for the first week. They may then increase to 20mg OD for the second week. A final increase to 30mg OD could be made in the third week. Treatment with amitriptyline will continue for a total of 6 months.

8.2.2 Dose Modification

After the first 3 weeks it is expected that most participants will continue on a steady dose of drug. However, the dose of amitriptyline can be modified throughout the study in response to side effects and to achieve normalisation of stool consistency and improvement of discomfort associated with diarrhoea. We expect most participants to find a dose that it suitable for them between 10mg OD and 30mg OD, but participants will be allowed to reduce their dose further, to 10mg every other day if they continue to experience troublesome side effects at 10mg OD. The maximum dose that patients will be allowed to take is 30mg OD. Standardised guidance on dose titration and modification will be provided to participants.

8.2.3 Assessment of Amitriptyline Adherence

Participants will be asked to record amitriptyline adherence via a self-reported summary question asked at 8 weeks and 6 months. To self-monitor adherence, a patient diary will be provided to participants following randomisation.

8.2.4 Amitriptyline Supply and Assessments

Participants will receive an initial 1-month supply of amitriptyline. This should allow for the maximum titration of amitriptyline in this time period. At each telephone call the research nurse should check to make sure there have been no changes to the participant contact details.

Week 1 Telephone Call:

Participants will be called at week 1 by their research nurse to deal with any queries and provide standardised advice about dose titration.

- Information to be collected:
 - Dose of study medication;
 - Toxicity assessment: collection of SAEs/SARs/SUSARs experienced since randomisation;
 - Concomitant medications check;

Week 3 Telephone Call:

Participants will be contacted by their research nurse by telephone at 3 weeks, to confirm the dose reached during titration and to ensure that there are no contraindications to further medication being issued.

- Information to be collected:
 - Dose of study medication;
 - Toxicity assessment: collection of SAEs/SARs/SUSARs experienced since week 1;
 - Concomitant medications check;
 - Suicidal ideation check: If there is any evidence of suicidal ideation, the participant must stop taking amitriptyline, no further amitriptyline should be issued and their GP should be informed of the need for urgent review to assess their mood and mental health;
 - o Confirm participant contact details;
 - Arrange for a further 2 months of trial treatment to be supplied, if appropriate.

Participants will be offered a review with their gastroenterologist (either via telephone or faceto-face) at approximately 1 month, for safety purposes (in relation to taking the study drug), if the research nurse or patient have any queries or concerns.

Month 3 Telephone Call:

A further telephone call from the research nurse will take place just before 3 months, to ensure that there are no contraindications to further medication being used.

- Information to be collected:
 - Dose of study medication;
 - Toxicity assessment: collection of SAEs/SARs/SUSARs experienced since week 8;
 - o Concomitant medications check;
 - Suicidal ideation check: If there is any evidence of suicidal ideation, the participant must stop taking amitriptyline, no further amitriptyline should be issued and their GP should be informed of the need for urgent review to assess their mood and mental health;
 - Confirm participant contact details;
 - Arrange for a final 3 months of trial treatment to be supplied, if appropriate.

At each telephone call the research nurse should check to make sure there has been no changes in the participant contact details.

8.2.5 Amitriptyline Toxicity

The most frequent anticipated toxicities of amitriptyline are as follows:

Aggression	Somnolence
Dizziness	Dry mouth
Headache	Constipation
Drowsiness	Nausea

For a full list of toxicities please refer to the latest SPC for amitriptyline.

8.3 Ondansetron

8.3.1 Dosage and Duration

Participants randomised to receive ondansetron will start on an initial dose of 4 mg (one capsule), OD. If symptoms do not improve then self-led dose titration may occur during the first 2 weeks on treatment. Participants will be given a dose guidance document to support self-titration and will also receive a telephone call from a research nurse on day 7 to offer support. The dose can be increased by 4mg (one capsule) every 2 days until a stable dose is achieved. The maximum dose of ondansetron is 8 mg three times per day (24mg per day, or six capsules daily). After the first 2 weeks the patient should continue on a steady dose of drug, unless a further change is required to achieve normalisation of stool frequency, as confirmed by discussion between the patient and the research team. Treatment with ondansetron will continue for a total of 6 months.

8.3.2 Dose Modification

The dose of ondansetron can be modified throughout the study to achieve normalisation of stool consistency and improvement of discomfort associated with diarrhoea. If a patient experiences constipation, they must stop taking ondansetron until a bowel movement occurs, and then restart at a lower dose. If required, the dose will be reduced to a minimum of one tablet per week. Participants unable to tolerate these minimal doses should discontinue ondansetron. Standardised guidance on dose titration and modification will be provided to participants.

8.3.3 Assessment of Ondansetron Adherence

Participants will be asked to record ondansetron adherence via a self-reported summary question asked at 8 weeks and 6 months. To self-monitor adherence, a patient diary will be provided to participants following randomisation.

8.3.4 Ondansetron Supply and Assessments

Participants receiving ondansetron will be provided with an initial 3-month supply of ondansetron. This should allow for the maximum titration of ondansetron in this time period. At each telephone call the research nurse should check to make sure there have been no changes to the participant contact details.

Week 1 Telephone Call:

Participants will be called at week 1 by their research nurse to deal with any queries and provide standardised advice about dose titration.

- Information to be collected:
 - Dose of study medication;
 - Toxicity assessment: collection of SAEs/SARs/SUSARs experienced since randomisation;
 - Concomitant medications check;

Week 3 Telephone Call:

Participants will be contacted by their research nurse by telephone at 3 weeks, to confirm the dose reached during titration

- Information to be collected:
 - Dose of study medication;
 - Toxicity assessment: collection of SAEs/SARs/SUSARs experienced since week 1;
 - Concomitant medications check;
 - Confirm participant contact details.

Participants will be offered a review with their gastroenterologist (either via telephone or faceto-face) at approximately 1 month, for safety purposes (in relation to taking the study drug),, if the research nurse or patient have any queries or concerns.

Month 3 Telephone Call:

A further telephone call from the research nurse will take place just before 3 months, for safety purposes, before a further 3 months of ondansetron can be dispensed.

• Information to be collected:

- Dose of study medication;
- Toxicity assessment: collection of SAEs/SARs/SUSARs experienced since week 8;
- o Concomitant medications check;
- Confirm participant contact details;
- Arrange for a final 3 months of trial treatment to be supplied, if appropriate

8.3.4 Ondansetron Toxicity

For a full list of toxicities please refer to the latest SPC for Ondansetron. The most common side effect for ondansetron is constipation.

8.4 Loperamide

8.4.1 Dosage and Duration

Participants randomised to receive loperamide will be given the option to use this as required, or to commence on 4mg per day (two capsules), and self-titrate the dose upwards to a maximum of 16mg per day (eight capsules), depending on symptoms, using the dose guidance document provided. Treatment with loperamide will continue for a total of 6 months.

8.4.2 Dose Modification

Participants can either use loperamide as required or modify their dose throughout the study, as desired, to achieve normalisation of stool consistency and improvement of discomfort associated with diarrhoea. Standardised guidance on dose titration and modification will be provided to participants.

8.4.3 Assessment of Loperamide Adherence

Participants will be asked to record loperamide adherence via a self-reported summary question asked at 8 weeks and 6 months. To self-monitor adherence, a patient diary will be provided to participants following randomisation.

8.4.4 Loperamide supply and Assessments

Participants receiving loperamide will be provided with an initial 3-month supply of trial medication. This should allow for the maximum titration of loperamide in this time period.

At each telephone call the research nurse should check to make sure there have been no changes to the participant contact details.

Week 1 Telephone Call:

Participants will be called at week 1 by their research nurse to deal with any queries and provide standardised advice about dose titration.

- Information to be collected:
 - Dose of study medication;
 - Toxicity assessment: collection of SAEs/SARs/SUSARs experienced since randomisation;
 - Concomitant medications check;

Week 3 Telephone Call:

At week 3, participants will be contacted by their research nurse by telephone to confirm the dosing strategy adopted by the participant (PRN or titrated) and the dose reached at the end of the titration period.

- Information to be collected:
 - Dose of study medication;
 - Dosing strategy (PRN or titrated);
 - Toxicity assessment: collection of SAEs/SARs/SUSARs experienced since week 1;
 - Concomitant medications check;
 - Confirm participant contact details.

Participants will be offered a review with their gastroenterologist (either via telephone or faceto-face) at approximately 1 month, for safety purposes (in relation to taking the study drug), if the research nurse or patient have any queries or concerns.

Month 3 Telephone Call:

A further telephone call from the research nurse will take place just before 3 months, for safety purposes, before a further 3 months of loperamide can be dispensed.

- Information to be collected:
 - Dose of study medication;
 - Toxicity assessment: collection of SAEs/SARs/SUSARs experienced since week 8;
 - Concomitant medications check;
 - Confirm participant contact details;
 - Arrange for a final 3 months of trial treatment to be supplied, if appropriate

8.4.4 Loperamide Toxicity

For a full list of toxicities please refer to the latest SPC for Loperamide.

The most common side effect for loperamide is constipation. If this happens participants should reduce their dose as per the dose guidance document. Loperamide may increase the risk of developing toxic megacolon in patients with inflammatory bowel disease, although this is very unlikely in patients with stable disease. However, participants are advised to contact their doctor/research nurses urgently if they develop abdominal (tummy) pain, fever, and a racing heart.

8.5 Standard Clinical Practice (All Arms)

All participants will continue their usual treatment for UC during the trial, and will be provided with the BDA IBS dietary advice sheet https://www.bda.uk.com/foodfacts/IBSfoodfacts.pdf), which is NICE-endorsed. They will be advised not to alter their diet in any other way, unless they are in the low FODMAP diet arm of the trial.

8.6 Concomitant Treatments

The use of prohibited and restricted concomitant medications will be reviewed prior to confirmation of eligibility according to section 5. Patients that are unable to stop taking prohibited medication will be unable to enter the study. Concomitant medication reviews will also take place on the week 1, week 3, and month 3 telephone calls, and confirmation that the patient is not taking any prohibited or restricted medication will be recorded on the CRF. It is the responsibility of the local PI (or delegate) to review any new concomitant medication at the study visit to confirm the patient's continuing suitability for the study.

Use of monoamine oxidase inhibitors (e.g. selegiline and moclobemide) and drugs that prolong the QT interval (e.g. amiodarone, terfenadine, or sotalol) are prohibited for the participant for the duration of the trial.

For management of concomitant therapies, please refer to the latest SPCs for amitriptyline, ondansetron and loperamide. Concomitant medications started prior to the study will be allowed to continue at a stable dose providing, in the opinion of the investigator, they are not likely to alter bowel habit or are prohibited (see section 5).

If participants require treatment for another non-gastrointestinal condition, their PI (or medically-trained doctor in sites with an IBD Nurse Specialist PI without a prescribing qualification) will review the new drug therapy to consider whether there is a risk that the drug may affect gastrointestinal symptoms. If this agent is deemed unlikely to influence gastrointestinal symptom reporting they will be allowed to commence it. However, if any new treatment is deemed to have a high chance of influencing gastrointestinal symptom reporting, then instances of this will be recorded and monitored, in order to assess whether there are equal rates among arms of the trial.

Use of loperamide in all non-loperamide arms of the study (amitriptyline, ondansetron, low FODMAP diet and control) is not permitted throughout the duration of the study.

As loperamide is available as an 'over the counter' medication as a well-known remedy for diarrhoea (Immodium) and participants are made aware of all the interventions used across the study, loperamide usage will be monitored across all non-loperamide arms.

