9.2.2 Treatment Arm Specific Assessments – Overview

For full details of the treatment specific assessments please see section 8 and the Schedule of Events. In summary:

Control Group: no additional assessments

Low FODMAP Arm:

- Face-to-Face appointments with the dietitian during week 1 and after week 8 for participants randomised to this arm.
- Telephone call (16 weeks) and face-to-face appointment (24 weeks) with dietitian for responders only. All participants (including non-responders) will also see a research nurse at 24 weeks as per section 9.2.2 below.

Drug Intervention Arms:

- Telephone calls from the research nurse at weeks 1 and 3, and month 3, postrandomisation. Please refer to the treatment specific guidance provided for each individual study drug in section 8 for details.
- Participant diary cards participants to record the number the number of tablets they have taken each day on diary cards from start to completion of study treatment. The diary cards are to be used as participant guidance so participants can monitor their own adherence to medication.

Assessments to be carried out for all patients in all arms are detailed below in section 9.2.3.

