9.2.2.1.2 Data Collection from Medical notes

The following data will be collected from the medical notes and recorded on the CRF:

- Confirmed flare of disease activity;
- Any requirement for escalation of UC-related medical therapy;
- Need for surgery.
- Collection of SAEs/SARs/SUSARs/RUSAEs experienced since randomisation;

9.2.2.2 6-month Face-to Face visit- All Participants 9.2.2.2.1 Patient Reported Questionnaires

Participants will self-complete a questionnaire booklet at 6 months post-randomisation. Participants completing questionnaires online will be sent the questionnaire via text message and/or email. Participants completing questionnaires on paper will be sent the questionnaire via post; the research nurse will contact the participants at 6 months to remind them to complete the booklets and return them. They will be sent an SMS reminder and an email to prompt completion. If the questionnaire has not been completed by the time the participant attends the 6-month face-to-face visit, they will be asked to complete it at the visit on paper.

Questionnaires will include:

- GSRS-IBS [26];
- IBD-Q [27];
- Tolerability;
- HADS [28];
- Need for either escalation of medical therapy for UC or surgery;
- CNAQ [34] (low FODMAP arm only).

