9.2.2.2.2 Face-to-Face Visit

At 6 months, participants will be invited to a final face-to-face appointment with a research nurse. Prior to this visit a stool sample collection kit should be sent to the participant.

The following assessments/data collection will be undertaken at face-to-face visit:

- Blood for CRP;
- Stool for FC;
- Any requirement for escalation of UC-related medical therapy;

- Need for surgery;
- Confirmed flare of disease activity.
- Dose of study medication for IMP arms
- SAE/SAR/SUSAR/RUSAE check
- Concomitant medications check.

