Appendix 5 Schedule of Events

Screening - Randomisation

TIMEPOINT	5	Screening	Baseline		
ASSESSMENTS	Pre-screening Call	Consent Visit	Screening	Baseline	
Verbal consent and preliminary evaluation of inlousion/ exclusion criteria	x				
Suicidal ideation	x			х	
Duration and extent of UC	x				
Written informed consent 1		х			RANDOMISATION
Registration		х			SAT
Medical history and medications			х		ž
tTG		2	x		ğ
FC, CRP ^{2,3}			x		RA
Flexible sigmoidoscopy ⁴			x	-	
Pregnancy test ⁵			x		
Confirm eligibility.				х	
GSRS	x			х	
IBD-Q	-			х	
CNAQ				х	
HADS				х	
Sociodemographic details, current meds, duration and extent of UC, previous or current psychiatric diagnoses				x	

1 Written Informed Consent must be obtained before blood test is carried out.

2 FC/CRP levels to be assessed within 4 weeks prior to randomisation.

3 If CRP result is abnormal, which may be a temporary abnormality, the blood test may be repeated approximately

1-2 weeks later if the participant wishes to undertake further screening for the study.

4 If required due to clinical uncertainty of UC stability or in the presence of rectal bleeding.

5 For women of child bearing potential. If hospital screening visit is >7 days prior to randomisation, a home pregnancy test

must be taken before a participant can be randomised.

Control group

TIMEPOINT		We	Month 6	
ASSESSMENTS		Patient complete	Nurse complete	Final visit
FC, CRP				х
Concomitant medication check	Z			
GSRS	Ĕ	х		Х
IBD-Q	JIS/	х		х
CNAQ	ő	х		
HADS	RANDOMISATION	х		x
Loperamide usage	2	x		x
Need for either escalation of medical therapy for UC		1.11.2	1.112.20	
or surgery;		x	x	x
SAE/SAR/SUSAR check			x	x
Check for flare of disease activity		о С	x	x

Amitriptyline

TIMEPOINT		Week 1	Week 3	Week 4	We	ek 8	Month 3	Month 6
ASSESSMENTS		Phone call	Phone call	Clinician review ¹	Patient complete	Nurse complete	Phone call	Final visit
Suicidal ideation			x				x	
FC, CRP								х
Concomitant medication check		х	х	20 X2	-	х	x	х
GSRS				92 - 53 -	х	8 - 1 - N		х
IBD-Q	Z				X			х
CNAQ	Ē				х			
HADS	ŝ			2 22	х			х
Loperamide usage	l õ			S 53	х	8		x
SAE/SAR/SUSAR (toxicity) check	RANDOMISATION	х	х	1	х	х	x	х
Need for either escalation of medical therapy for UC or surgery;	2				x	x		x
Adherence (via diary card)					x			х
Unused medication return								х
Study medication replenish			х				x	
Optional clinican review				х				
Contact details check		x	x				x	
Dose information		x	x				x	x
Check for flare of disease activity						х		х

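### Section 8.6 plans to compare new symptom-influencing treatments between arms, but scheduled medication checks by week 8 number three in each drug arm, one in the diet arm and none in control

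*Protocol*

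**What the plan says.** Section 8.6 (Concomitant Treatments) deals with drugs started during the trial for non-gastrointestinal conditions. The principal investigator or a doctor reviews each one. If it is judged likely to affect symptom reporting, "instances of this will be recorded and monitored, in order to assess whether there are equal rates among arms of the trial". The same section schedules routine reviews: "Concomitant medication reviews will also take place on the week 1, week 3, and month 3 telephone calls".

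Section 9.2.2 lists those contacts, "Telephone calls from the research nurse at weeks 1 and 3, and month 3", under the drug arms only. For control it says: "Control Group: no additional assessments".

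Appendix 5 carries a row labelled "Concomitant medication check" in every arm's table. In the amitriptyline, ondansetron and loperamide tables it is marked at weeks 1, 3 and 8 and months 3 and 6. In the low FODMAP table it is marked at week 8 and month 6. In the control table no time point is marked.

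Section 9.2.2.1.2 sets out the week-8 notes review for all participants ("The following data will be collected from the medical notes and recorded on the CRF"). It lists flare, escalation of UC therapy, surgery and serious events, but not concomitant medication. Section 9.2.2.2.2 lists "Concomitant medications check" at the 6-month visit for everyone.

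Loperamide is handled separately: "loperamide usage will be monitored across all non-loperamide arms". Appendix 5 marks that item at week 8 and month 6 in all four non-loperamide arms.

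**The concern.** A comparison of recorded rates says something about true rates only if each arm is searched with similar intensity. Here the intensity follows the safety contacts, which differ by arm. The arm searched least is control, which has 132 of the 396 phase 2 participants (section 13.1.1) and is the comparator for all four interventions.

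The trial is open label with self-reported outcomes (section 4.1), so a reader of the final report will want to know whether participants in one arm took other drugs that act on the bowel. With unequal searching, a real excess in control could be hidden, or an excess in the drug arms could appear where none exists. The statistical analysis plan cannot repair this later, because the gap is in what is collected.

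**Working it through.** **Step 1: count the scheduled checks per participant.**

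| Reading | Each drug arm | Low FODMAP | Control |
|---|---|---|---|
| By week 8, Appendix 5 | 3 (weeks 1, 3, 8) | 1 (week 8) | 0 |
| By week 8, body text only (sections 8.6, 9.2.2, 9.2.2.1.2) | 2 (weeks 1, 3) | 0 | 0 |
| By week 8, if the control row has lost a week-8 mark | 3 | 1 | 1 |
| By month 6, Appendix 5 | 5 | 2 | 0 |
| By month 6, Appendix 5 with section 9.2.2.2.2 applied to control | 5 | 2 | 1 |

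On every reading the drug arms have more checks than control.

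**Step 2: what unequal checking does when true use is equal.** Let k be the number of scheduled checks, p the chance that one check picks up a start, and q the chance that it is recorded without a scheduled check (investigator review or unprompted report). Take p and q as equal in all arms. Then

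share of true starts recorded = 1 − (1 − q)(1 − p)^k.

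The protocol gives neither p nor q, so the following is an illustration with p = 0.6 and q = 0.3.

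By week 8, Appendix 5 counts:
- drug arm: 1 − 0.7 × 0.4³ = 1 − 0.0448 = 0.955, about 96%
- low FODMAP: 1 − 0.7 × 0.4 = 0.72, or 72%
- control: 1 − 0.7 × 1 = 0.30, or 30%

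With p from 0.3 to 0.9 and q from 0 to 0.9, the recorded shares are 66–100% (drug), 30–99% (diet) and 0–90% (control).

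By month 6 with 5, 2 and 1 checks, p = 0.6 and q = 0.3:
- drug arm: 1 − 0.7 × 0.4⁵ = 0.993, about 99%
- low FODMAP: 1 − 0.7 × 0.4² = 0.888, about 89%
- control: 1 − 0.7 × 0.4 = 0.72, or 72%

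**Step 3: limits of the illustration.** Using k = 3 in the drug arms assumes a start early enough for all three checks to see it. A start after the week-3 call can be seen by only one check by week 8, so the counts become 1, 1 and 0 and the shares 72%, 72% and 30%. The drug-versus-diet gap closes for such starts, but the gap with control stays. If control really has a week-8 mark, the early-start shares are 96%, 72% and 72%.

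**Step 4: equal checking.** If k is the same in every arm, the formula gives the same share in every arm for the same p and q, so equal true rates give equal expected recorded rates.

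**The case against.** The strongest reply is that section 8.6 describes two processes. The week 1, week 3 and month 3 reviews exist to confirm that no prohibited or restricted drug is being taken. The between-arm comparison belongs to a different paragraph, triggered whenever a participant needs a new drug for a non-gastrointestinal condition, and that route is open to every arm. Table 2 in section 12 also says participants will be asked to tell the research nurse about new treatments. This stands in part. A reader might infer that control has no record at all by week 8, and the protocol does not support that: what control lacks is a scheduled check. The event route still depends on someone raising the new drug, the drug arms are asked more often, and the Table 2 instruction sits in the rows about the trial drugs.

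Second, the blank control row may be a loss in reading the table, since a row with no marks serves no purpose. That is possible and should be checked against the original. It would change the week-8 counts to 3, 1 and 1, which leaves drug and control unequal. A reader might also infer that control is never checked; section 9.2.2.2.2 gives it a month-6 check, so that reading fails.

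Third, the likeliest contaminants are already covered. Loperamide use is asked evenly in the non-loperamide arms, and escalation of UC therapy is collected in all arms at week 8 and month 6 from both questionnaires and notes (sections 9.2.2.1.1 to 9.2.2.2.2 and 13.2.3.2). This stands and narrows the point to other new drugs.

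Fourth, nothing inferential uses the tally. It is not an endpoint in section 13.2, and section 13.3.6 bases progression on the p-value and, if more than two arms qualify, on response rates and safety. This also stands. The protocol never says the check informs the week-8 decision, so it cannot be faulted for failing to do so.

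**Conclusion.** The point holds as a limited defect in data collection. The protocol sets out to judge whether new symptom-influencing treatments are balanced between arms, and its schedule searches for them 3, 1 and 0 times by week 8 in each drug arm, the diet arm and control. By month 6 the counts are 5, 2 and either 0 or 1, because Appendix 5 and section 9.2.2.2.2 disagree. The expected direction is under-recording in control, if the chance of detection per check and of unprompted reporting is similar across arms.

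The size is unknown. A reader might take the worst case as the result: if 10% of every arm started such a drug, 6.6 of 66 would be recorded in a drug arm and 0 of 132 in control, where 13.2 occurred. That 10-point gap needs full detection in the drug arms and none in control, and the protocol supports neither. If unprompted reporting is near complete, the bias is small.

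The consequence is confined to this descriptive balance check, leaving aside loperamide use and UC-therapy escalation. The primary effect estimates and the stated phase 2 progression rule are not affected.

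**What to change.** - Add one identical new-medication item, with the same look-back period, to the week-8 and month-6 assessments in all five arms. It can sit beside the loperamide-usage question where that exists, but the loperamide arm's table has no such row and needs the item as well.
- In Appendix 5, mark the check for control at week 8 and month 6, which also reconciles the table with section 9.2.2.2.2. Add concomitant medication to the week-8 notes review in section 9.2.2.1.2.
- State in section 8.6 that the between-arm comparison uses only these common time points, and that data from the week 1, week 3 and month 3 calls are kept for safety review.

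The cost is one extra item and a schedule correction, with no new visit or staff. Recall over the look-back period will be less complete than repeated calls, but the method is the same in every arm. Earlier calls might still prompt better recall in the drug arms, so some smaller difference could remain.
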